10.2 Analysis of Secondary Objective

10.2.1 For the area under the curve of pain scores at 48 hours, prior studies have found that the area under the curve for pain scores at 72 hours for liposomal bupivacaine infiltration is $441 +/- 182$ and for bupivacaine infiltration is $461 +/- 181^{20}$. A sample size of 40 in each group will have 80% power to detect a difference in means of approximately 25% (115 units) between a Bupivacaine mean, m_1 , of 461 and a Liposomal Bupivacaine mean, m_2 , of 346 assuming that the common standard deviation is 181 using a two group t-test with a 0.05 two-sided significance level. Our study will be powered to detect this difference; we will use an independent t-test to assess statistical significance.

10.2.2 For postoperative narcotic use, prior studies have found the average use of morphine equivalents at 48 hours after mastectomy and tissue expander placement is 3.3¹⁷. This study will also have the ability to detect an effect size of 0.6 between groups, with 45 per group, a two-sided alpha of 0.05, and 80% power. We would expect the patients treated with liposomal bupivacaine to be have a lower average use. We will use an independent t-test to test for differences between groups; if the data are not normally distributed, a log transformation will be used prior to using the t-test.

10.2.3 For length of stay, the reported LOS has been shown to be 41-47 hours on average²¹. We believe Exparel will shorten this time; the study will have the ability to detect an effect size of 0.60 between the 2 groups. We will use an independent t-test to test for differences between groups; if the data are not normally distributed, a log transformation will be used prior to using the t-test.

10.2.4 For readmission rates, patients who underwent tissue expander breast reconstruction have a readmission rate of approximately 4.34%²². We anticipate a readmission rate of approximately 2%. Our study is not powered to detect differences in the 2 arms in this parameter.

10.2.5 For opioid related adverse effects, we predict a 50% incidence of opioid related adverse events in our study. With 45 per group, our study is not powered to detect differences between the 2 arms unless the difference is much larger than anticipated. With a 60%

THE USE OF LIPOSOMAL BUPIVACAINE FOR PAIN CONTROL FOLLOWING
MASTECTOMY AND IMMEDIATE IMPLANT BASED BREAST RECONSTRUCTION

Wake Forest Baptist Comprehensive Cancer Center
CCCWU # 99517

rate, 2-sided alpha of 0.05 and 80% power, we could detect a difference of 31% between the 2 arms using a Fisher's Exact Test

- 10.2.6 For trajectory of postoperative recovery from pain, Growth curve analysis of pain intensity with movement scores over the first two months, using an initial log (time) model and a Bayesian change point analysis
 - 10.2.6.1 Groups will be compared for intercept and slope of the trajectory of pain intensity up to the first change point
 - 10.2.6.2 For the entire population, the impact of the optimism-catastrophizing continuum and other predictive factors for intercept and slope will be explored

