In an effort to decrease pain control, it is common practice for local anesthetics to be infiltrated into the surgical wound. Individual studies have shown that infiltrations with bupivacaine specifically have decreased intraoperative and postoperative narcotic use, decreased pain scores in the immediate postoperative period²⁴⁻²⁶. However, upon meta-analysis of randomized clinical trials studying the effect of wound infiltration with bupivacaine or ropivacaine it was found that postoperative pain severity was only decreased at 2 hours postoperatively and postoperative analgesic consumption did not change²⁷. In light of this, there continues to be a need for improvement in postoperative pain management for mastectomy and subsequent breast reconstruction.

One such medication which has been suggested for improvement in pain control after mastectomy and breast reconstruction is Exparel (Pacira Pharmaceuticals, Inc., San Diego, CA). It is a relatively recent bupivacaine multi-vesicular liposomal delivery system that allows slow release of bupivacaine, resulting in local anesthetic effects for up to 72-96 hours after injection. It is a safe pain control modality with a similar side effects profile to bupivacaine HCL and does not compromise breast implant integrity¹³⁻¹⁴.

Side effects of Exparel primarily includes GI upset (nausea and vomiting) which can occur in greater than 10% of patients. More rare side effects include hypotension (2-10%), insomnia (2-10%), pruritus (3%), postoperative anemia (2-10%), and muscle spasm (2-10%). Similar to other local anesthetics, dose related toxicity can occur and can lead to central nervous system excitation or depression. Exparel has a half-life of 24-34 hours and is hepatically metabolized and renally excreted. It should be used in caution with patients with moderate-severe hepatic or renal impairment because of the increased risk of toxicity. Exparel may increase the toxicity of lidocaine and bupivacaine. Bupivacaine can be administered with or immediately before Exparel as long as the milligram dose ratio of bupivacaine to Exparel is not greater than 1:2. Furthermore, Exparel may increase the effect of neuromuscular blocking agents. Exparel is not recommended in pregnant patients as there have been no studies conducted in this population and high doses used in animal models have been shown to decrease fetal

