5.2 Secondary Outcomes

5.2.1 Area under the curve visual analog scores (scale 0-10) during the first 48 hours postoperatively.

5.2.1.1 For patients undergoing submuscular augmentation mammoplasty, the area under the curve for pain scores at 72 hours for liposomal bupivacaine infiltration is 441 +/- 182 and for bupivacaine infiltration is 461 +/- 181²⁰

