The study will be double blinded to both patients and providers including plastic and general surgeons involved in their operative care. We will enroll our patients in pharmacy randomization program, in which the pharmacy will deliver the appropriate medication per assigned group.

To monitor our primary outcomes, patients will be asked to rate their pain level on a visual analog scale (Table 2, Appendix Z) with activity every 12-hours after surgery during their post-procedure stay. The activity for which they will rate their pain will be the arm movements associated with eating. In the hospital, their visual analog scores will be provided to each patient in person by their nurse every 12 hours. Subject's pain scores will continue to be recorded every 12 hours via a phone call from a study team member for the first 48 hours after discharge. Additionally, while in the hospital, the amount of narcotics used will be recorded and converted into morphine equivalents.

Upon discharge, patients will be given a sheet to record their pain level and the amount of narcotics & benzodiazepines used (Appendix K). Both the amount of narcotics & benzodiazepines and the pain level are to be reported at the time of taking any narcotics & benzodiazepines. Patients will follow up with our clinic at 1 week, 3 weeks, and 5 weeks postoperatively. At week 1 patients will bring in their medication and pain diary, and fill out a pain assessment (Appendix G) in addition to a questionnaire assessing breast cancer surgery

THE USE OF LIPOSOMAL BUPIVACAINE FOR PAIN CONTROL FOLLOWING MASTECTOMY AND IMMEDIATE IMPLANT BASED BREAST RECONSTRUCTION

Wake Forest Baptist Comprehensive Cancer Center
CCCWU # 99517

disability (Appendix H)²³. During subsequent appointments made at 3 and 5 weeks postoperatively, they will be assessed and receive the pain assessment and breast cancer surgery disability assessments as well. When tissue expansion is initiated will be determined by the primary surgeon, but we will track the dates of the initiation of expansion as this will impact pain scores within the electronic medical record.

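### The power statement for the 48-hour pain AUC (10.2.1) uses a mean, SD and target difference from a 72-hour AUC without converting them

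*Combined protocol and SAP*

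**What the plan says.** Section 5.2.1 defines the outcome as "Area under the curve visual analog scores (scale 0-10) during the first 48 hours postoperatively", and objective 2.2.1 uses the same window. Section 10.2.1 opens on that window too: "For the area under the curve of pain scores at 48 hours". The only reference data it then gives are for a longer window: "the area under the curve for pain scores at 72 hours for liposomal bupivacaine infiltration is" 441 (SD 182), and for bupivacaine 461 (SD 181). Section 5.2.1.1 gives the population of that study: "For patients undergoing submuscular augmentation mammoplasty".

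From these values 10.2.1 takes a bupivacaine mean of 461, a liposomal mean of 346, a difference of 115 units (about 25%) and a common SD of 181. It states that 40 per group give 80% power with a two-group t-test at two-sided 0.05, and that the study will be powered for this difference. Significance is to be assessed by an independent t-test. Section 10.3 plans 25 per arm, and 10.1.1 allows for 10% attrition.

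**The concern.** An AUC grows with the length of its window, so a 72-hour mean, SD and difference cannot stand in for 48-hour ones. Here the substitution puts the assumed control mean close to the top of the 48-hour scale, which signals that the window was overlooked rather than deliberately approximated.

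At stake is whether the power claim can be read at all. A reader who takes 115 units as a 25% reduction in 48-hour AUC misjudges the pain difference the trial is said to be able to detect. The 48-hour SD, which drives the sample size, is not given anywhere in the documents.

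**Working it through.** **Inputs.** Window 48 h (2.2.1, 5.2.1, 10.2.1). Reference window 72 h, bupivacaine mean 461, SD 181, target 115, 40 per group, two-sided 0.05, 80% power (10.2.1). Planned 25 per arm (10.3). Attrition 10% (10.1.1). Assumption: the AUC is in score-hours on the 0-10 scale. The documents do not state the unit of the cited values.

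**1. Reproduce the plan's figure.** Effect size d = 115/181 = 0.635. The normal approximation n = 2 × (1.960 + 0.842)² / d² gives 38.9, so 39. The exact noncentral-t calculation gives 39.87, so 40, with power 80.1% at 40 per group. The stated 40 is correct for the inputs used.

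**2. Test the inputs against the 48-hour scale.**
- Maximum AUC: 10 × 48 = 480 (over 72 h, 10 × 72 = 720).
- Mean pain implied by 461: 461/72 = 6.4 over 72 h, but 461/48 = 9.6 over 48 h.
- Largest possible SD for a variable on 0 to M with mean m is √(m(M − m)). For m = 461 and M = 480 this is √(461 × 19) = 93.6. An SD of 181 cannot occur in the bupivacaine arm.
- For the liposomal mean of 346 the bound is √(346 × 134) = 215, so 181 is not excluded there. It is the common SD that fails.
- 115 units over 48 h is 115/48 = 2.4 points of mean pain. Over 72 h it is 115/72 = 1.6 points.

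**3. Rescale to 48 hours.** With constant average pain the factor is 48/72 = 0.667.
- Control mean 461 × 0.667 = 307
- Liposomal mean 346 × 0.667 = 231
- 25% difference 115 × 0.667 = 77
- SD 181 × 0.667 = 121, if the SD is proportional to time

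The effect size is then 76.7/120.7 = 0.635, as before, and n stays at 40. Keeping 115 units on this scale would be 115/307 = 37% of the control mean, not 25%.

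**4. Range for the unknown 48-hour SD,** at 77 units. The middle row scales by the square root of time, 181 × √0.667 = 148. The last row leaves the SD unchanged.

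| 48-h SD | Effect size | n per group for 80% | Power at 25 per arm |
|---|---|---|---|
| 121 | 0.635 | 40 | 60% |
| 148 | 0.519 | 60 | 44% |
| 181 | 0.424 | 89 | 31% |

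After 10% attrition (25 × 0.9 = 22.5 per arm) the first row falls to about 55%.

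**5. Difference detectable with 80% power at 25 per arm.** The detectable effect size is 0.809. At SD 121 this is 0.809 × 120.7 = 98 units, or 98/48 = 2.0 points of mean pain.

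**The case against.** The strongest reply is that the slip has no effect on the analysis. The 115 units appear only in the power statement, the test is an ordinary t-test on the observed AUCs, and under proportional rescaling the effect size and the 40 per group do not move. All of that stands. What remains is that the printed mean and SD cannot both hold on the outcome's own scale, and that n = 40 survives only if the SD shrinks in full proportion to time, which the plan does not say.

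A second reply is that the unit of the cited AUC is not given. That is fair. But the outcome is defined on a 0-10 score, 461 over 72 hours gives a plausible 6.4 in score-hours, and mixing windows is wrong in any unit.

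A reader might also infer more than the documents support:

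- **That 115 units is a bar the result must clear.** Section 10.2.1 sets no such threshold, and a smaller difference can be significant.
- **That the target is about twice the difference the protocol expects.** The 5.0 and 4.8 in 5.1.1.1 come from patients on oral and IV narcotics, and the 3.8 in 5.1.1.2 from a different cited study. Neither pair is this trial's contrast.
- **That a 48-hour AUC merely repeats the primary.** This fits 5.1.1, where the primary is the mean over 48 hours. It fails if the primary is the single 48-hour score named in 10.1.1.
- **That the outcome should move to 72 hours because the data will exist.** Section 6.1 does say that "pain scores will continue to be recorded every 12 hours via a phone call from a study team member for the first 48 hours after" the patient leaves hospital, and 1.0 describes the product as "resulting in local anesthetic effects for up to 72-96 hours after injection". But 5.1.1 describes 12-hourly scoring only to 48 hours after surgery. A patient discharged before 24 hours would not reach 72 hours (about 16% if stay were normal with the 36 ± 12 h of 5.2.3.2). Because 5.2.3.2 expects shorter stays only in the liposomal arm, that loss could differ by arm. Starting the AUC at 12 hours would leave a 60-hour window and bring the mismatch back.

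**Conclusion.** The point holds as an error in the stated inputs of a secondary-outcome power statement. In score-hours, a 48-hour control mean of 461 means pain of 9.6 out of 10 and caps the SD at about 94, against the 181 assumed. On the rescaled control mean, 115 units is a 37% reduction rather than 25%. The test is valid as planned, and 40 per group stands under proportional scaling.

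The conclusion rests on score-hour units. The rescaled values also rest on roughly constant pain over 72 hours. If pain falls over time, the first 48 hours carry more than two thirds of the area and 307 is too low. Rescaling corrects the window only. The values still come from augmentation mammoplasty.

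The gap between 40 per group in 10.2.1 and 25 per arm in 10.3 is a separate defect. It bears on this point because a restated power claim has to use the planned number.

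**What to change.** Keep the 48-hour outcome in 2.2.1 and 5.2.1, and rewrite the inputs of 10.2.1 on that window:

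- State the AUC unit and that the cited values cover 72 hours.
- Give the control mean as about 307, the 25% difference as about 77 units and the SD as about 121, each marked as rescaled by 48/72.
- Declare the SD scaling as an assumption and show the range: SD 121, 148 or 181 needs about 40, 60 or 89 per group.
- Replace the claim that the study is powered for this difference with the power at 25 per arm: about 60% at SD 121, lower at the larger SDs.

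A 72-hour AUC may be added as a supportive analysis where scores exist, once 5.1.1 and 6.1 are reconciled on how long 12-hourly scoring continues.

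The cost is a few sentences in 10.2.1, with no new assessments and no change to the test. The price is an open statement that power for this outcome is well below 80%.

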10.0 Statistical Considerations

10.1 Analysis of Primary Objective

10.1.1 The study will allow for an attrition rate of 10%. Assuming a similar standard deviation in pain score at 48 hours for the local infiltration of liposomal bupivacaine and bupivacaine arms, with a 2-sided alpha of 0.05 and power of 80%, the study would have the ability to detect an effect size (absolute value of difference in sample means divided by the standard deviation) of 0.6 between the 2 groups with 25 subjects per arm. We will recruit 25 subjects per arm; if there is no attrition, with the same alpha and power as above, the study would have the ability to detect an effect size of 0.57. The primary outcome will be the pain score observed at 48 hours. To test for differences in these scores between the 2 arms, an independent t-test will be used; if the observed p-value is <0.05, statistical significance will be assumed. Two-sided ANOVA will be performed for statistical analysis once data collection is complete.

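### The secondary power figures in Section 10.2 hold at 40 to 45 patients per group, but the trial has 25 per arm; power for the AUC difference is about 60%, not 80%

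*Combined protocol and SAP*

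**What the plan says.** **Trial size.** Section 10.1.1: "We will recruit 25 subjects per arm". Sections 10.3 and 10.4 confirm 50 patients in total. Section 10.1.1 also says: "The study will allow for an attrition rate of 10"%.

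**AUC (10.2.1).** "A sample size of 40 in each group will have 80% power to detect a difference in means of approximately 25% (115 units"), from means of 461 and 346 with a common SD of 181 and a two-sided 5% t-test. The next sentence reads: "Our study will be powered to detect this difference; we will use an independent t-test to assess statistical significance". The planning values are 72-hour figures; the outcome in 5.2.1 covers 48 hours.

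**Opioid use (10.2.2).** The study is said to have the "ability to detect an effect size of 0.6 between groups, with 45 per group, a two-sided alpha of 0.05, and 80% power".

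**Length of stay (10.2.3).** "the study will have the ability to detect an effect size of 0.60 between the 2 groups". No sample size, alpha or power is given.

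**Opioid adverse effects (10.2.5).** "With 45 per group, our study is not powered to detect differences between the 2 arms unless" the true difference is well above what is expected. From a 60% rate, with Fisher's exact test and 80% power, "we could detect a difference of 31% between the 2 arms".

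Nothing in the document explains how a 50-patient trial would supply 40 to 45 patients per group.

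**The concern.** A power statement describes the trial only if it uses the trial's own sample size. Here the secondary calculations use 80 to 90 patients in total and the design has 50. For AUC the plan goes further and says outright that this study is powered for the difference.

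What is at stake is how the results are read. A reader who trusts the plan would expect a 20% chance of missing the stated differences. At 25 per arm the chance is about 40% for AUC and 45% for a 0.60 effect on opioid use or length of stay, before attrition. A non-significant result would then say much less than the plan implies.

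**Working it through.** **Inputs.** AUC difference 115 and SD 181 (10.2.1); effect size 0.60 (10.2.2, 10.2.3); 60% rate and a 31-point difference (10.2.5); two-sided alpha 0.05; 25 per arm (10.1.1, 10.3); 10% attrition (10.1.1). Attrition leaves 50 × 0.9 = 45 patients, so 22 v 23, or 22 per arm if both arms are rounded down.

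**Method for means.** Noncentral t with n per arm: noncentrality = d × √(n/2), degrees of freedom 2n − 2. For proportions, Fisher's exact test by full enumeration.

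**Step 1: reproduce the plan's figures.**
- AUC: d = 115/181 = 0.635. The n for 80% power is 39.9, so 40. At n = 40 the noncentrality is 0.635 × √20 = 2.84 and power is 80.1%.
- Effect size 0.60: n = 44.6, so 45. At n = 45 power is 80.4%.
- Fisher, 60% v 29%, n = 45: power 79.0%; 80% is reached at a fall of just over 31 points.

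The formulas are sound. Only the sample size is out of line.

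**Step 2: the same calculations at the trial's size.** For AUC at n = 25 the noncentrality is 0.635 × √12.5 = 2.25; for d = 0.60 it is 2.12.

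| Quantity | Plan's n | 25 per arm | 22 v 23 | 22 per arm |
|---|---|---|---|---|
| Power, AUC 115 units | 80.1% (40) | 59.5% | 54.9% | 53.9% |
| Power, d = 0.60 | 80.4% (45) | 54.7% | 50.3% | 49.4% |
| d detectable with 80% power | 0.597 (45) | 0.809 | 0.855 | 0.865 |
| AUC units detectable (d × 181) | 115 (40) | 146 | 155 | 157 |
| Power, Fisher 60% v 29% | 79.0% (45) | 53.6% | not run | 42.5% |
| Fall from 60% detectable | about 31 points (45) | 40.5 points | not run | about 44 points |

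As a share of 461, the detectable AUC difference is 146/461 = 32% at 25 per arm and 155/461 = 34% at 22 v 23, against the plan's 25%. Taking 23 in both arms gives 55.9% AUC power. A one-sided AUC test at 25 per arm reaches only 71.6%.

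**Step 3: length of stay in hours.** Section 5.2.3 gives 41 to 47 h in earlier patients and 36 h ± 12 expected with liposomal bupivacaine. Treating ±12 as a common SD is my assumption. Then d = 5/12 = 0.417 gives 30% power and d = 11/12 = 0.917 gives 89% at 25 per arm (27% and 84% at 22).

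**Step 4: the 72-hour scale.** If AUC is score × hours on a 0–10 scale (the document gives no unit), the 48-hour maximum is 10 × 48 = 480, so a mean of 461 is not plausible. Proportional scaling by 48/72 gives mean 307, SD 121 and difference 77. Power is unchanged, and the detectable difference is 98 units at 25 per arm and 104 at 22. If the SD shrinks less than the mean, power for 77 units at 25 per arm falls: 44% with SD 148 (square-root scaling) and 31% with SD 181.

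**The case against.** The strongest objection is that the mismatch does not start in Section 10.2. Section 10.1.1 attaches effect sizes of 0.6 and 0.57 to 25 per arm, yet these are the detectable effects at 45 (0.597) and 50 (0.566) per arm. Section 3.3 equates 5% with 5 patients and 10% with 10, which implies 100 in total: 50 per arm, 45 after 10% attrition. On this reading the secondary figures come from a coherent 100-patient plan and the 25s are what is out of step. That stands as a possible explanation, though it is an inference. It does not rescue Section 10.2, because the document now gives 25 per arm in three places. It does mean that correcting 10.2 alone would leave 0.6 in 10.1.1 beside 0.81 in 10.2.

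Smaller points that also stand:
- Section 10.2.3 gives no sample size, so its dependence on 45 per group is inferred from the shared 0.60.
- Section 10.2.5 already concedes low power, so only its sample size and the 31 points are wrong. It gives no direction either: a rise from 60% would need about 35 points at 25 per arm. A fall is the reading that reproduces the plan's 31.
- The length-of-stay power range is too wide to support a conclusion by itself.
- The 72-hour values are openly labelled as such, and proportional scaling leaves power unchanged.

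None of these changes the result for AUC or for the 0.60 effect.

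**Conclusion.** The concern holds. With 25 per arm, the claim that the study is powered for a 115-unit AUC difference is wrong: power is 59.5%, and 54% to 55% after attrition. For opioid use and length of stay, the effect detectable with 80% power is 0.81 (about 0.86 after attrition), not 0.60. For opioid adverse effects, the detectable fall from 60% is about 41 points (44 at 22 per arm), not 31.

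These results use the plan's own inputs and tests. They assume that 25 per arm is the current design, that 10.2.3 shares the alpha and power of 10.2.2, and that the 31 points are a fall from 60%. The hour-based length-of-stay powers and the 48-hour AUC figures rest on the further assumptions given with them. Only secondary outcomes are affected here, so this should be corrected but does not by itself undermine the trial. Section 10.2.4 claims no power and is not affected.

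**What to change.** First confirm whether 25 per arm is the intended size. If it is:

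1. Delete the sentence in 10.2.1 saying that the study will be powered for the AUC difference.
2. Restate 10.2.1, 10.2.2, 10.2.3 and 10.2.5 for 25 per arm, with and without 10% attrition, using the table above.
3. Put the AUC assumptions on the 48-hour scale, give the unit, and label the scaling as an assumption.
4. Say which arm or population the 60% adverse-effect rate in 10.2.5 describes, and how it relates to the 50% there and the 30% in 5.2.5.2.
5. If power for length of stay is quoted, show it across the whole 41 to 47 h range.
6. Restate the 0.6 and 0.57 in 10.1.1 at the same time, so that the primary and secondary sections agree, and align the counts in 3.3.

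The cost is protocol wording only, with less favourable figures. No analysis changes. If a larger trial is intended, the sample size in 10.1.1, 10.3 and 10.4 must change instead, with the accrual and study length that follow from it.

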5.2.2 Morphine equivalents used within the first month postoperatively

THE USE OF LIPOSOMAL BUPIVACAINE FOR PAIN CONTROL FOLLOWING MASTECTOMY AND IMMEDIATE IMPLANT BASED BREAST RECONSTRUCTION

Wake Forest Baptist Comprehensive Cancer Center
CCCWU # 99517

- 5.2.2.1 The number of doses of oral narcotics (hydrocodone-acetaminophen 1 tablet) for patients with immediate tissue expander reconstruction without other measure of pain control has been 4.2 at 24 hours and 4.0 at 48 hours¹⁷. This is approximately 3.3 morphine equivalents
- 5.2.2.2 We would expect the patients treated with liposomal bupivacaine to use an average of 2.5 intravenous morphine equivalents at the 48-hour point and decreased morphine equivalents in the liposomal bupivacaine over the first postoperative month.
- 5.2.3 Length of stay for hospitalization after mastectomy and breast reconstruction
 - 5.2.3.1 Length of stay for patients undergoing mastectomy and immediate reconstruction has been shown to be 41-47 hours on average²¹
 - 5.2.3.2 We believe liposomal bupivacaine will shorten this time to 36 hours±12 in the liposomal bupivacaine group, but not in the bupivacaine groups.
- 5.2.4 Readmission rates to the hospital within 2 months after mastectomy and breast reconstruction
 - 5.2.4.1 Patients who underwent tissue expander breast reconstruction have a readmission rate of approximately 4.34%²². We anticipate a readmission rate of approximately 2% Patients will be informed that if they are expected to undergo an axillary lymph node dissection at the time of surgery then they will be excluded from the study. Patients who are undergoing sentinel lymph node biopsies will be included in the study, but if their nodes are positive and there is an intraoperative decision to pursue axillary lymph node dissection they will subsequently be excluded from the study.
- 5.2.5 Frequency of postoperative opioid related adverse effects within the first week of surgery. This includes nausea, vomiting, pruritus, allergy, respiratory depression.
 - 5.2.5.1 After immediate breast reconstruction with implants, patients receiving bupivacaine had a 40% incidence of nausea and vomiting. Those not receiving a local anesthetic had a 75% incidence of nausea and vomiting¹⁷
 - 5.2.5.2 We predict a 30% incidence of opioid related adverse events in our liposomal bupivacaine group
- 5.2.6 Trajectory of postoperative recovery from pain within the first 2 months

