10.3 Power and Sample Size

We will have a power of 80%, as described in 10.1.1, with a sample size of 25 patients in each arm for a total of 50 patients

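### Fisher's exact test for opioid adverse effects is valid but conservative. A prespecified Boschloo test would recover a little power at the same 5% level, and the 31-point detectable difference needs restating for 25 per arm.

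*Combined protocol and SAP*

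**What the plan says.** Section 10.2.5 covers opioid related adverse effects, a secondary outcome counted over the first postoperative week (section 5.2.5). It makes three statements:

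- Expected rate: "we predict a 50% incidence of opioid related adverse events in our study". Section 5.2.5.2 adds, for one arm: "We predict a 30% incidence of opioid related adverse events in our liposomal bupivacaine group".
- Power: "With 45 per group, our study is not powered to detect differences between the 2 arms unless the difference is much larger than anticipated".
- Detectable difference, starting from a 60% rate, with two-sided alpha 0.05 and 80% power: "we could detect a difference of 31% between the 2 arms using a Fisher's Exact Test".

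Fisher's test appears only in that last sentence. Since nothing else is named for this outcome, taking it as the planned analysis is a reasonable inference, though the plan does not say so outright.

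The planned size is smaller than the 45 used there. Section 10.3 gives 80% power "with a sample size of 25 patients in each arm for a total of 50 patients", and section 10.1.1 allows 10% attrition.

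**The concern.** Fisher's test conditions on both margins of the 2x2 table. With few patients the possible p-values are widely spaced, so the test usually cannot spend its full 5%. The plan already concedes that this outcome is short of power, so unspent error is a loss that could be reduced without more patients or data.

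Boschloo's unconditional test takes the Fisher p-value as its statistic and sets the cut-off so that the maximum error over all common event rates is at most 5%. Every table that Fisher rejects is also rejected, so power cannot fall.

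The detectable difference in the same sentence is a separate matter. It is calculated for 45 per group, not for the 25 per arm that will be recruited, and this affects the sentence more than the choice of test does.

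**Working it through.** **Inputs.** Two-sided alpha 0.05, target power 80%, reference rate 60%, difference 31 points (so 60% v 29%) and 45 per group, all from 10.2.5. Planned 25 per arm, from 10.1.1 and 10.3. Attrition 10%, from 10.1.1, which gives 25 × 0.9 = 22.5, or about 22-25 evaluable per arm.

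**Method.** All 2x2 tables (x events of n1, y of n2, t = x + y) are enumerated.

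- Fisher p(x,y) = sum of h(k) over all k with h(k) ≤ h(x), where h(k) = C(n1,k)·C(n2,t−k)/C(n1+n2,t). Reject if p ≤ 0.05.
- True error at common rate π = ΣΣ b(x;n1,π)·b(y;n2,π)·1{reject}, maximised over π from 0.001 to 0.999.
- Boschloo: reject if Fisher p ≤ c, where c is the largest cut-off with maximum error ≤ 0.05. With equal arms of 22, 23, 24 and 25, c = 0.0946, 0.0746, 0.0798 and 0.0792.
- Power = ΣΣ b(x;n1,0.60)·b(y;n2,0.29)·1{reject}.

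**The plan's own figure.** At 45 per group Fisher's power for 60% v 29% is 79.0%, and the difference detectable with 80% power is 31.4 points. The stated 80% and 31 points are therefore reproduced for 45 per group. At that size Fisher's maximum error is 3.2%, and Boschloo's power is 84.2%.

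**Exactly equal arms, 60% v 29%.**

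| Per arm | Fisher max error | Boschloo max error | Fisher power | Boschloo power | Gain (points) |
|---|---|---|---|---|---|
| 22 | 2.44% | 4.97% | 42.5% | 54.9% | 12.4 |
| 23 | 2.60% | 4.75% | 46.3% | 56.2% | 9.9 |
| 24 | 2.94% | 4.90% | 50.0% | 57.9% | 7.8 |
| 25 | 3.28% | 4.63% | 53.6% | 56.7% | 3.1 |

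**Unequal arms within 22-25, 60% v 29%** (first number is the arm with the 60% rate).

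| Split | Fisher max error | Fisher power | Boschloo power | Gain (points) |
|---|---|---|---|---|
| 23 v 22 | 3.7% | 49.9% | 52.9% | 3.0 |
| 22 v 23 | 3.7% | 51.2% | 53.5% | 2.3 |
| 23 v 24 | 4.0% | 54.9% | 55.3% | 0.4 |
| 25 v 23 | 4.0% | 56.6% | 57.1% | 0.5 |
| 24 v 25 | 4.4% | 58.4% | 58.6% | 0.3 |

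Over all unequal splits in this range, in both directions, Fisher's maximum error is 3.7-4.4% and the gain is 0.3-3.0 points.

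**Version of the two-sided test.** The result that power never falls belongs to the version above, which orders tables by the two-sided Fisher p-value. Doubling a one-sided 2.5% Boschloo test gives identical results with equal arms. With several unequal splits it no longer contains Fisher's rejection region. Its gain there was about 0 to 4.4 points in these cases, but the guarantee is lost.

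**Detectable difference from 60% with 80% power.** At 25 per arm it is 40.5 points with Fisher and 38.7 with Boschloo. At 22 per arm it is 44.0 and 40.4 points.

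**Other rates, 25 per arm.** For 50% v 30%, an illustrative pairing of the study-wide and liposomal-arm predictions, power goes from 23.2% to 28.2%. For 40% v 30%, it goes from 7.0% to 10.8%. The 40% is the nausea and vomiting rate with bupivacaine in 5.2.5.1, which is narrower than the composite outcome.

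**The case against.** Fisher's test is standard and controls the type I error. Being conservative on a single secondary outcome is defensible, particularly where no multiplicity control is described. All of that stands, and it rules out calling the choice an error.

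A reader might infer from the equal-arm table that Fisher's true error here is simply 2.4-3.3% and that changing the test buys 10-12 points of power. The documents do not support that, for two reasons:

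- **Equal arms are not assured.** Section 6.1 mentions a pharmacy randomisation program but describes no blocking. It also excludes patients who need an unplanned axillary dissection, and those losses need not balance. Once the arms differ by even one patient, Fisher's maximum error is 3.7-4.4% and the gain is at most about 3 points.
- **The 10% attrition is stated alongside the pain outcome.** Section 6.1 says adverse opioid effects are followed through the electronic medical record, so missed diaries or phone calls need not remove patients. If all 25 per arm are evaluable, the gain is 3.1 points.

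A reader might also infer that Boschloo's test makes the comparison adequately powered. It does not: power for the plan's own contrast at 25 per arm is still 56.7%, and "our study is not powered to detect differences between the 2 arms" remains true.

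Nor should the change be carried over to readmission. Section 10.2.4 names no test and declares no power. At 4.34% v 2% with 22-25 per arm, power is about 1% or less even with Boschloo.

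What survives is narrower: the same error guarantee, power that is never lower, and almost no cost.

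**Conclusion.** The point holds as an optional efficiency gain on a secondary outcome that stays underpowered. At the planned 25 per arm and 60% v 29%, replacing Fisher with Boschloo adds about 3 points of power. The gain is about 0-3 points with unequal arms of 22-25, and reaches 8-12 points only with exactly equal arms of 22-24.

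The larger matter in the same sentence is the sample size. The 31-point difference is right for 45 per group. At 25 per arm Fisher has 53.6% power for it, and no choice between these two tests restores 80%.

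The conclusion assumes that Fisher is the intended analysis, that the two arms are independent binomials, and that 22-25 patients per arm are evaluable.

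**What to change.** In section 10.2.5, before unblinding:

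1. Name a two-sided Boschloo exact test at 0.05 for the arm comparison, and state that it orders tables by the two-sided Fisher p-value, so that the software's two-sided definition is fixed in advance.
2. Report the risk difference with an unconditional exact or score-type 95% confidence interval. The section specifies none, and an interval tells the reader more than a p-value in an underpowered comparison.
3. Restate the detectable difference for 25 per arm: about 39 points from 60% with Boschloo, or 40.5 points if Fisher is kept. Item 3 is needed whichever test is chosen.

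The cost is a few sentences in the plan, with no extra patients or data. The downside is a test that some readers know less well. Timing matters, because choosing the more powerful test after seeing the data would not be credible.
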